5.5 Guidelines for Ibrutinib Management with Surgeries or Procedure

Ibrutinib may increase risk of bleeding with invasive procedures or surgery. The following guidance should be applied to the use of ibrutinib in the perioperative period for patients who require surgical intervention or an invasive procedure while receiving ibrutinib:

5.5.1. Minor Surgical Procedures

For minor procedures (such as a central line placement, needle biopsy, thoracentesis, or paracentesis) ibrutinib should be held for at least 3 days prior to the procedure and should not be restarted for at least 3 days after the procedure.

5.5.2. Major Surgical Procedures

For any surgery or invasive procedure requiring sutures or staples for closure, ibrutinib should be held at least 7 days prior to the intervention and should be held at least 7 days after the procedure and restarted at the discretion of the investigator when the surgical site is reasonably healed without serosanguineous drainage or the need for drainage tubes.

5.5.3. Emergency Procedures

For emergency procedures, ibrutinib should be held after the procedure until the surgical site is reasonably healed, for at least 7 days after the urgent surgical procedure.

6. Visit schedule and assessments

6.1 Pretreatment Evaluation

Baseline tumor and patient characteristics including:

- Patient demographics: age, gender and race
- Medical history;
- Medications;
- ECOG performance status;
- Type of neuroendocrine tumor: primary site (if known) vs. unknown;
- Differentiation or grade (if available);
- Known sites of metastases;
- Presence or absence of hormonal syndrome (carcinoid syndrome, gastrinoma syndrome, insulinoma syndrome, etc.);
- Presence or absence of a pathologically elevated hormone or biomarker;
- EORTC QLQ C-30 and EORTC QLQ GI-NET21 questionnaires.

Tests to be performed within 28 ±2 days prior to initiation of therapy (if day 28 falls on a weekend or holiday the deadline may be extended to the next working day):

- Radiologic assessment of tumor burden by CT scan or MRI; In all cases, imaging studies should encompass the abdomen and any other known sites of measurable disease. For small bowel NETs, imaging of the abdomen and pelvis is recommended. For pancreatic NETs, abdominal imaging is sufficient if there are no known extra abdominal sites. For lung NETs, imaging of the thorax and abdomen is recommended.
- Assessment of secretory proteins. All patients will undergo an initial assessment of chromogranin A. Patients with suspected serotonin-producing tumors (and all patients with midgut carcinoid tumors) will have a 24 hour urine 5-HIAA measured at baseline. Other possible neuroendocrine tumor markers/hormones (e.g. pancreatic polypeptide,

gastrin, glucagon, etc.) may be collected at the discretion of the investigator based on clinical symptoms and tumor location.

Tests to be performed within 14 ±2 days prior to initiation of therapy (if day 14 falls on a weekend or holiday the deadline may be extended to the next working day):

- History and physical evaluation including height, weight, vital signs and performance status;
- Baseline hematological and biochemical profiles including CBC with differential and comprehensive metabolic panel (fasting glucose, sodium, potassium, calcium, chloride, bicarbonate, creatinine, blood urea nitrogen, albumin, SGOT (AST) SGPT (ALT) total bilirubin and alkaline phosphatase);
- Serum pregnancy test for women of childbearing potential;
- Correlative laboratory studies with the potential to correlate with response to the treatment (measurement of serum Tryptase-β2).

6.2 Evaluations During Treatment

Beginning of every cycle (defined as 28 ±2 days):

- Physical examination;
- Toxicity assessment;
- Vital signs;
- Weight;
- ECOG performance status;
- CBC with differential;
- Fasting comprehensive metabolic panel;
- Assessment of adverse events.

Data to be obtained every 3 cycles ±1 week of treatment until disease progression, unacceptable toxicity or withdrawal of consent:

- Radiologic assessment of tumor burden by CT scan or MRI;
- Assessment of chromogranin A and/or other tumor markers or hormones if elevated at baseline (see section 6.1);
- EORTC QLQ C-30 and EORTC QLQ GI-NET21 questionnaires;
- Correlative laboratory studies (see section 6.1).

Patients who have an ongoing grade 4 or serious adverse event at the time of discontinuation from study drug treatment will continue to be followed at no less than monthly intervals, until resolution of toxicity to less than grade 2.

6.3 Instructions for processing correlative laboratory studies

Correlative laboratory studies will include the assessment of blood- and tissue-based biomarkers with the potential to correlate with response to treatment.

6.3.1 Blood-based biomarkers

Blood will be collected every three months. Serum measurement of Tryptase- β 2 will be performed by ELISA in the Translational Research Core of the Moffitt Cancer Center.

6.3.2 Tissue-based biomarkers:

If available, archival tissue containing a tumor block (preferred) or 10 unstained slides (3-5 micron thick) from patient's primary or metastatic neuroendocrine tumor should be sent to Moffitt Cancer Center for correlative immunohistochemical studies. Specimens should be placed in a secure, airtight container, labeled with the patient name and study number.

Site should contact Moffitt Cancer Center at [contact] with expected delivery date.

Shipping address:

Attention [name]
Anatomic Pathology Dept.
H. Lee Moffitt Cancer Center
[name]
[name]

Immunohistochemistry (IHC) will be used to evaluate the expression of c-kit, tryptase and chymase as markers for mast cell presence and activation, respectively. Sections of 3-4 microns in thickness will be cut from the selected formalin-fixed paraffin embedded tissue and subjected to IHC staining protocol using the Dakocytomation Autostainer (DakoCytomation, Carpinteria, Calif). Microwave antigen retrieval with IHC Select EDTA buffer, pH 7.5, will be utilized. Primary antibodies with cross-reactivity against the human subtypes of the above mentioned targets will be diluted and incubated for 60 minutes at room temperature. Using a semiquantitative scoring system, the intensity of IHC staining for c-kit, chymase and tryptase will be scored as either 0 (negative), 1+ (mild positive staining), 2+ (moderate positive) and 3+ (strong positive staining). The correlation between staining patterns and clinical outcomes (response rate or PFS) will be analyzed in a descriptive fashion.

6.4 Evaluation schema

Table 6-5 lists all of the assessments and indicates the visits at which they are to be performed with an "X". All data obtained from these assessments must be supported in the patient's source documentation.

Table 6-5 Visit evaluation schedule

Evaluation	Screening/ Baseline ^a	Each Cycle (day 1 \pm 2)	Every 3 Cycles \pm 1 week (until disease progression, unacceptable toxicity or withdrawal of consent)	End ^b
Informed consent	X			
Demographics	X			
Relevant medical	X	X		X

history/ current medical conditions				
Diagnosis and extent of cancer	X			
Physical exam	X	X		X
Vital signs	X	X		X
ECG ^c	X			
ECOG Performance Status	X	X		X
CBC with differential ^d	X	X		X
Glycosylated hemoglobin	X			
Fasting Comprehensive metabolic panel ^e	X	X		X
Pregnancy test and review of contraception ^f	X			
Secretory hormones ^g and serum chromogranin A	X		X	X
Radiologic assessment of tumor burden ^h	X		X	X
Adverse events ⁱ	X	X		X
Concomitant medications ^j	X	X		X
EORTC QLQ C-30 and EORTC QLQ GI-NET21 questionnaires	X		X	
Correlative laboratory studies ^k	X		X	

^a Screening includes review of: demography/informed consent, inclusion/exclusion criteria, relevant medical history/concomitant medications, diagnosis and extent of cancer.

^b Patients who interrupt or permanently discontinue ibrutinib due to an adverse event or abnormal laboratory value must be followed at no less than monthly intervals, until resolution of toxicity to less than grade 2. These patients will be censored, and tumor assessment will be performed off trial at treating physician's discretion.. Patients will be followed for OS each 12 months using their charts or the Social Security Death Index.

^c ECG should be done at any time when clinically indicated.

^d Complete blood count must include: hemoglobin, hematocrit, platelets, total white blood cell count and differential.

^e Comprehensive metabolic panel should include fasting glucose, sodium, potassium, calcium, chloride, bicarbonate, creatinine, blood urea nitrogen, albumin, total protein, SGOT (AST), SGPT (ALT), total bilirubin and alkaline phosphatase.

^f For women of child-bearing potential: women of childbearing potential must have a negative serum pregnancy test within 14 days of enrollment. Acceptable contraception must be used while on study and for at least 60 days after last dose of ibrutinib.

^g If patients present with hormonally active tumor, secretory hormone levels corresponding to the syndrome (e.g. urine 5-HIAA, gastrin, glucagon, insulin, etc.) should be measured at baseline, at each restaging cycle and at the end of study treatment.

^h Baseline radiologic tests (CT or MRI with iv contrast) should include all known sites of metastatic disease. For most midgut carcinoid tumors, a CT or MRI scan of the abdomen and pelvis is indicated. For pancreatic neuroendocrine tumors, a CT or MRI scan of the abdomen may be sufficient. Radiological scans documenting target lesions should be repeated every 3 cycles (12 weeks). The same type of scan should be used at each evaluation.

ⁱ See section 9.1 for definitions of adverse events.

^j All concomitant medications, including over the counter drugs, should be documented each visit.

^k Correlative laboratory studies will include measurement of serum Tryptase β2.

7. Outcome Measures

The primary efficacy endpoint is objective response rate as determined by radiology review.

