5.4 Interruption or Discontinuation of Treatment

Patients may be removed from study for the following reasons:

- Documented disease progression or symptomatic tumor progression. In the case of symptomatic tumor progression, all efforts should be made to document disease status radiologically prior to removal from study;
- Occurrence of unacceptable toxicity (see table 5-2 regarding dose modifications for toxicity). Patients removed from treatment for intolerable toxicity should still be followed with regular tumor assessments until disease progression or start of a new treatment;
- Patient has been off treatment for >3 weeks;
- The patient chooses to terminate participation in the study;
- At the discretion of the investigator;
- If, at any time, the constraints of this protocol are detrimental to the patient's health and/or the patient no longer wishes to continue protocol therapy, protocol therapy shall be discontinued. In this event the study chairs should be notified, the reasons for discontinuation should be documented, and the patient should be followed as appropriate per study.

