7.3 Confirmation Measurement/Duration of Response

Confirmation: To be assigned a status of PR or CR, changes in tumor measurements must be confirmed by repeat studies that should be performed no less than 4 weeks after the criteria for response are first met. In the case of SD, follow-up measurements must have met the SD criteria at least once after study entry at a minimum interval of 6 weeks. Progression of disease should be verified in cases where progression is equivocal. If repeat scans confirm PD, then progression should be declared using the date of the initial scan. If repeat scans do not confirm PD, then the subject is considered not to have progressive disease per RECIST 1.1.

Duration of Overall Response: The duration of overall response is measured from the time measurement criteria are met for CR/PR (whichever is first recorded) until the first date that recurrent or progressive disease is objectively documented (taking as reference for progressive disease the smallest measurements recorded since the treatment started).

The duration of overall complete response is measured from the time measurement criteria are first met for CR until the first date that recurrent disease is objectively documented.

Duration of Stable Disease: Stable disease is measured from the start of the treatment until the criteria for progression are met, taking as reference the smallest measurements recorded since the treatment started.

Progression Free Survival (PFS): PFS is defined as the time from the date of first study treatment to the date of the first documented disease progression or death due to any cause. If a patient has not progressed or died at the date of the analysis cut-off or when he/she receives any further anti-cancer therapy, PFS is censored at the time of the last tumor assessment before the cut-off or the anti-cancer therapy date.

Time to Treatment Failure: Time from administration of the initial dose of ibrutinib until study discontinuation for any reason (e.g. disease progression, toxicity, death, withdrawal of consent).

Biochemical marker response will be defined as $\geq 50\%$ reduction in tumor marker from baseline.

8. Statistical Considerations

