8.2 Endpoints to be followed

Efficacy Endpoints

- Tumor response rate using RECIST (Primary endpoint);
- OS, determined from the time of drug administration to death from any cause (Secondary endpoint);
- PFS, determined as the time from administration of the initial dose of ibrutinib until objective tumor progression using RECIST, or death (Secondary endpoint);
- Duration of response, defined as time from first observation of an objective response which is subsequently confirmed, to first disease progression or death due to any cause (Secondary endpoint);
- Changes in health-related quality of life, as assessed by EORTC questionnaires EORTC QLQ-C30 and QLQ GI.NET21 (see section 11).

Safety Endpoint

Safety assessments will consist of monitoring and recording all adverse events and serious adverse events, the regular monitoring of hematology and blood chemistry parameters and regular physical examinations. Adverse events will be evaluated continuously throughout the study. Safety and tolerability will be assessed according to the NIH/NCI Common Terminology Criteria for Adverse Events version 4 (CTCAE v4) available at: http://ctep.cancer.gov/protocolDevelopment/electronic_applications/ctc.htm. All adverse events will be documented on the adverse event CRF.

Exploratory Analyses (refer to Section 6.3)

As part of this study, we will explore the correlation between early biochemical response and response rates or PFS. Early biochemical responders will be defined as patients with elevated chromogranin A (CgA) who experience a major reduction (>50%) or normalization of their CgA between their baseline (pretreatment) measurement and their follow-up assessment 3 months later.

We also plan to undertake an exploratory analysis of blood- and tissue-based markers that may correlate with the clinical outcomes observed in the study. Exploratory markers will include the measurement of serum Tryptase- β 2 and the determination of the presence and activation of mast cells in the tumor tissue samples.

Archival pathology specimens will be reviewed at the study institution (Moffitt Cancer Center) for determination of mitotic rate (number of mitoses per 10 high-powered fields) and Ki-67 index.

This study is not sufficiently powered to establish definitive outcome for the correlative endpoints. These results will be considered hypothesis generating and any comparison with a significant alpha <0.05 will be deemed of sufficient interest to warrant further evaluation.

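### Table 6-5 footnote b censors patients who stop ibrutinib for toxicity and moves their scans off trial, contradicting Section 5.4 follow-up and the Section 7.3 and 8.2 PFS definitions

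*Combined protocol and SAP*

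**What the plan says.** All references are to the combined protocol and SAP.

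- **Table 6-5, footnote b (Section 6.4)**, attached to the End column, covers "Patients who interrupt or permanently discontinue ibrutinib due to an adverse event or abnormal laboratory value". It states "These patients will be censored, and tumor assessment will be performed off trial", at the treating physician's choice. It names no endpoint. It goes on to provide yearly OS follow-up from charts or a death index.
- **Section 5.4**: "Patients removed from treatment for intolerable toxicity should still be followed with regular tumor assessments until disease progression or start of a new treatment".
- **Section 7.3**: PFS runs to the "date of the first documented disease progression or death due to any cause". A patient without an event is censored in two situations only, the analysis cut-off or further anti-cancer therapy: "PFS is censored at the time of the last tumor assessment before the cut-off or the anti-cancer therapy date".
- **Section 8.2**: "PFS, determined as the time from administration of the initial dose of ibrutinib until objective tumor progression using RECIST, or death". Duration of response is the "time from first observation of an objective response which is subsequently confirmed, to first disease progression or death due to any cause". Neither definition mentions stopping for toxicity. The Section 7.3 definition of duration of response ends at documented recurrence or progression and does not mention death.
- **Section 6.2 and the every-3-cycles column of Table 6-5** schedule scans only until progression, unacceptable toxicity or withdrawal of consent. The table adds an End scan. Section 6.4 states that "Table 6-5 lists all of the assessments".
- **Section 8.3** specifies Kaplan-Meier estimation for OS, PFS and duration of response.

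**The concern.** There are two conflicts. On follow-up, a site cannot both keep a patient on regular trial assessments (Section 5.4) and leave imaging off trial to the treating physician (footnote b). On analysis, a toxicity stop is not one of the Section 7.3 censoring situations, yet footnote b makes it one.

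Because footnote b keeps OS follow-up going, its censoring can bear only on PFS and duration of response. Duration of response has no other censoring rule. A patient who stops for toxicity and dies before any new therapy is a PFS event under Sections 7.3 and 8.2, but a censored observation under footnote b, with the death already in the database. A progression after the stop may never be recorded, because no schedule carries the assessments that Section 5.4 asks for.

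At stake are median PFS, 1-year PFS and duration of response, all secondary endpoints without a hypothesis test. If stopping is related to prognosis, the censoring is informative and the Kaplan-Meier estimate is biased. Scans that were not taken cannot be recovered at analysis.

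**Working it through.** **Step 1. The texts side by side, for a patient who stops for toxicity and has started no new therapy**

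| Question | Footnote b | Sections 5.4, 7.3, 8.2 | Section 6.2 and Table 6-5 schedule |
|---|---|---|---|
| Trial scans after the stop? | No, off trial | Yes, to progression or new therapy (5.4) | None after the End scan |
| Censored for PFS because of the stop? | Yes | No | Silent |
| Later death a PFS event? | No | Yes | Silent |
| Later death ends duration of response? | No | Yes under 8.2; 7.3 does not mention death | Silent |

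The plan gives no toxicity-stop rate and no PFS assumption, so it has no figure of its own to reproduce for PFS. The sizes below are illustrations.

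**Step 2. Assumed inputs.** Exponential PFS with a median of 11.4 months (the sunitinib figure for pNETs in Section 1.1, applied here to both cohorts); 10%, 20% or 30% stopping by 12 months; 24 months of follow-up for everyone. Monthly hazard h = ln 2 / 11.4 = 0.0608. Monthly stop rate m = -ln(1 - d)/12, so d = 20% gives m = 0.0186.

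**Step 3. PFS events lost, hazard unchanged after the stop**

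- Followed to event: 1 - exp(-24h) = 0.768, or 23.0 of 30 and 16.1 of 21.
- Footnote b: h/(h + m) × [1 - exp(-24(h + m))]. At 20%: 0.0608/0.0794 × [1 - exp(-1.906)] = 0.652.
- Loss at 20%: 1 - 0.652/0.768 = 15%.

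| Stopping by 12 months | Events of 30 (carcinoid) | Events of 21 (pNET) | Lost |
|---|---|---|---|
| 10% | 21.3 | 14.9 | 8% |
| 20% | 19.6 | 13.7 | 15% |
| 30% | 17.9 | 12.5 | 22% |

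Sensitivity for 10%, 20% and 30% stopping: with a median of 5.5 months (the control figure in Section 1.1) the losses are 6%, 11% and 17%. With 12 months of follow-up they are 5%, 9% and 14%. If half of those who stop start new therapy at once, Section 7.3 censors them too, and the losses are 4%, 8% and 13%.

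**Step 4. Bias in 12-month PFS, 20% stopping.** Kaplan-Meier censored at the stop estimates exp(-12h) = 48.2%. With the hazard multiplied by k after stopping, true PFS is S(12) = exp(-12(h + m)) + integral from 0 to 12 of m·exp(-(h + m)u)·exp(-kh(12 - u)) du.

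- k = 2: S(12) = 45.3%, overstated by 2.9 points.
- k = 1: S(12) = 48.2%, no bias, only lost precision.
- k = 0.5: S(12) = 50.3%, understated by 2.1 points.

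**Step 5. Sampling error for comparison.** The 95% half-width is 1.96 × sqrt(V/n), with V = exp(-24h) × integral from 0 to 12 of h·exp((h + m)u) du. Without stop-censoring (m = 0), it is 17.9 points for n = 30 and 21.4 for n = 21. With footnote b at 20% stopping, it is 19.1 and 22.8.

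**Step 6. Confirmed ORR.** Exact two-stage binomial on the Section 8.3 rules reproduces the plan: carcinoid alpha 5.8% and power 80.0%; pNET alpha 8.0% and power 80.3%. A responder is lost if the stop falls before confirmation. The fraction lost is f = 1 - exp(-w × rate), with rate = -ln(1 - d)/52.18 per week and w weeks of exposure, and the response rate becomes p(1 - f).

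| | Carcinoid power (p = 18%), 10-30% stopping | pNET power (p = 20%), 10-30% stopping |
|---|---|---|
| End scan done and counted (w = 4) | 79.5-78.1% | 79.8-78.7% |
| No End scan, confirmation at next 12-week scan (w = 12) | 78.4-74.2% | 78.9-75.2% |

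Responses first seen at or after the End visit are not modelled.

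**The case against.** The strongest reply is that Section 7.3 is the endpoint definition and an analyst would apply it over a table footnote. That supports using Section 7.3 for PFS censoring, but no text says so, and the schedules agree with footnote b. An analyst who applied Section 7.3 would still lack scheduled post-stop scans.

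A second reply is that the two rules often coincide. Section 7.3 censors at the last tumor assessment, so a patient with no recorded event and no trial scans after stopping is censored at or near the same date either way. This stands, and it narrows the divergence to deaths and to progressions found off trial. Only for deaths would two analysts certainly reach different counts from the same database.

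Third, the word for interruption in footnote b might be taken to censor everyone who is held and restarted under Section 5.2. The documents do not establish that. The footnote sits on the End column and may mean only interruptions that end participation. No figure here depends on that reading.

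Fourth, these are descriptive single-arm secondary summaries. That is correct, and it limits the weight of the point.

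**Conclusion.** The contradiction is in the current text and should be resolved. Its clear effect is confined to median PFS, 1-year PFS and duration of response. Under the assumptions in the working, 8-22% of PFS events are lost at a median of 11.4 months and 24 months of follow-up. At 20% stopping, the bias in 12-month PFS runs from +2.9 points (hazard doubled) through zero to -2.1 points (hazard halved), all inside a 95% half-width of about 18-21 points. Stop rates, post-stop hazards and follow-up are assumed, not taken from the plan.

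A reader might infer that footnote b inflates PFS. The documents give no basis for a direction, because it depends on the hazard after stopping.

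A reader might also infer that the primary endpoint is compromised. If the End scan is done and counted, the power loss is under 2 points. Only if footnote b also removes that scan, and confirmation waits for the next 12-week scan, does power fall to about 78-74% (carcinoid) and 79-75% (pNET). The text does not settle which applies.

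**What to change.** Reconcile Sections 5.4, 6.2, 7.3 and 8.2 with Table 6-5.

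1. In footnote b, replace the censoring statement with one saying that stopping or interrupting ibrutinib for toxicity is not in itself a censoring event and that Section 7.3 governs PFS censoring.
2. State one censoring rule of the same form for duration of response.
3. Count deaths found in OS follow-up as events wherever the definitions in Sections 7.3 and 8.2 do.
4. State one rule for tumor assessment after a toxicity stop, the same in Section 5.4, Section 6.2 and Table 6-5, at an interval the sponsor sets. The documents point both ways on this, so the choice is the sponsor's.
5. Say whether the End scan and any off-trial scans count toward response and progression.

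Items 1 to 3 and item 5 cost wording only. Item 4 costs wording plus, if the sponsor keeps the Section 5.4 requirement, any scans beyond the Section 6.2 schedule.
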